6.8.4 Other Therapy

There can be physiotherapy to improve the return to daily life and sport.

7 DISCONTINUATION OF TRIAL INTERVENTION AND PARTICIPANT WITHDRAWAL FROM TRIAL

7.1 Discontinuation of Trial Intervention

7.1.1 Criteria for Permanent Discontinuation of Trial Intervention

This is an orthopedic trial. The surgery is the start point and after the surgery there is no further treatment. There are only follow-up visits, which include an MRI (after 6 weeks, 6, 12, 24 months and 5 years in the operated group and after 24 months and 5 years in the non-operated group) and 3 questionnaires (IKDC and KOOS, CRF).

Criteria for permanent discontinuation for **single patients** from the trial are the following:

- Withdrawal of the informed consent
- lost to follow-up,
- premature death
- progression of osteoarthritis up to TKA
- the patient wishes to change to the operated group after a certain time

When withdrawal of the informed consent, premature death or lost to follow-up occurs, data up to the point will be used. If progression of osteoarthritis up to TKA occurs, the treatment is counted as treatment failure. These patients cannot continue the trial. Data up to the point will be used.

If the patient changes his decision and want to be operated at a later time point, the patient can continue the trial, but will be allocated to the other study arm. Data collected up to this point will be used in the first treatment group and then data will be generated in the second treatment group.

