3.3 Exploratory Objective + Associated Endpoint and Estimand

| Exploratory Objective | Exploratory Endpoint |
|--|---|
| How many patients show a progression of osteoarthritis up to TKA | Progression of osteoarthritis up to TKA |

Exploratory Estimand (Variable): Progression of osteoarthritis up to TKA

Endpoint: 2 and 5 years after surgery/enrollment

Treatment: varies with the group chosen by the patient (operated or not operated)

Population: male and female patients between 18 and 60 years

Intercurrent event: lost to follow-up, premature death

Population-level summary: the explorative objective is: how many patients have a progression of osteoarthritis up to TKA, in the operated and non-operated group.

Estimand Description:

The number of patients with progressing of osteoarthritis up to TKA will be evaluated using the Kaplan Meier estimator for time to event.

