9.2.1 Statistical Model, Hypothesis, and Method of Analysis

The change in PROMS from baseline in the operated and non-operated group will be compared by two-sided t-test for independent groups when data are normally distributed or with the Mann-Whitney-U-test.

The Null-hypothesis is that partial meniscal replacement does not improve mean PROMs for knee function in comparison to the non-operated group after 2 and 5 years.

The alternative hypothesis is that there that partial meniscal replacement does improve mean PROMs for knee function in comparison to the non-operated group after 2 and 5 years.

The PROMS should improve (Mean KOOS and IKDC should increase by at least 20 points, and VAS-pain score should decrease by at least 3 points, or to near zero, depending on the pre-surgical value).

Analysis of data will be performed by direct comparison of the groups at each time point and in comparison, to before surgery/start of the trial. Mean and standard deviation of the groups are compared. If there is a significant difference, the Null-Hypothesis will be rejected. Even when we have a loss of follow-up of 20% the power will still be 0.985. From our experience mean KOOS values presurgical are between 40-50 and between 50-60 for the IKDC, after treatment the expected improvement is to mean values between 80-90 for both scores. For the VAS-pain-score the presurgical mean value is around 4 and the post-surgical value is between 0 and 1. There is no risk of a type 1 error, because the values are measured several times over the follow-up period, thus there will be no false positive result. If the difference in the scores between pre- and post-surgery is lower than 18, the power is not big enough. Thus setting 20 as the difference for rejecting the Null-hypothesis is supported by enough power, even with only 8/24 patients in the respective group. The covariate could be smoking and sex. Smoking affects healing in general. It is not clear if there will be enough patients in each group to use these as confounders. Interactions will not be possible, because the treatment has no relation to any characteristic of the patient. There will be no adjustment made and no model fitting.

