9.2.2 Handling of Intercurrent Events of Primary Estimand(s)

Intercurrent events are: progression of osteoarthritis up to TKA, lost to follow up, premature death, the patient wishes to change to the operated group after a certain time. (as stated under point 3).

Data obtained until the event will be included in the analysis, last observation will be included in the evaluation. In case of progression of osteoarthritis up to TKA the procedure will be noted as fail. Premature death will be treated as lost to follow-up. Lost to follow-up and premature death can be unrelated to knee problems. If the patient wishes to change the treatment group, data are collected for this treatment up to the last treatment. If more than 20 % of patients fail, the benefit-risk balance will be re-evaluated, and it will be decided if the trial will be continued.

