9.3 Analysis Supporting Secondary Objective(s)

Secondary objectives are:

Safety of the patient, efficacy of the procedure, MRI image description and patient satisfaction.

Patient safety will be analyzing the number of AE, SAE and SUSARs and will be compared for both groups. The numbers obtained will be compared in a Chi-Square test. SUSARs will only occur, if any, in the operated group and thus cannot be compared to any other value. For categorial variables. Efficacy of the procedure will be analyzed by counting the number of failed procedures in the operated group. Because this value will only be determined in the operated group, there is no statistical analysis. The efficacy of the procedure must be over 80%. If the failed procedures are higher than 20 % the benefit-risk balance will be re-evaluated. The MRI signal will be evaluated after a modified scheme of Genovese [32]. The size of the meniscus and the amount of extrusion of the meniscus will be measured and recorded in both groups. The obtained numbers will be compared to the other group at the same time point and to the value before surgery/at the beginning of the trial. This will be performed with an unpaired t-Test if the values are normally distributed or with the Mann-Whitney-U-test for not normally distributed values. Patient satisfaction is a categorial value and will be only evaluated in the operated group. The number of patients who are very pleased, pleased, not pleased, very unsatisfied will be described by means of frequency tables and plots.

Intercurrent event are: progression of osteoarthritis up to TKA, lost to follow-up, premature death, the patient wishes to change to the operated group after a certain time. If these events happen, the data will be available until the event. Last date recorded will be analyzed. Progression of osteoarthritis up to TKA will be recorded as fail and will be reported as this. Patients changing to the operated group will be analyzed up to the date of change in the non-operated group. Missing data will not be estimated. A drop-out rate (lost to follow-up, premature death) of 20% is expected and accepted.

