9.7 Interim Analyses

Interim analysis will be performed 2 years after surgery/start of the trial. After knee surgery, the usual follow up is 2 years. Because long term results are important for the efficacy of the procedure, evaluations will be performed also after 5 years. The analysis will be performed by the investigator. The statistical methods used are described under 9.2 and 9.3. The outcome data will be seen only by the investigator while the trial is ongoing. The 2-years result will be published in an international orthopedic journal. There will be no group sequential test and no spending function. The number of patients is fixed at 30 in the operated group and at 10 in the non-operated group. There will be no enrollment until an event occurs. There will be no trial adaptation or changes to the eligibility criteria.

Stopping criteria are: If AE, SAE and SUSARs change the benefit-risk balance, there will be a new benefit-risk balance evaluation and after this evaluation it will be decided if the trial will be stopped. The investigator expects a maximal 20% failure rate of the procedure. If the failure rate is higher a new benefit-risk balance evaluation must be performed and after the evaluation it must be decided if the trial continues. If the safety of the patients is not any more given, the trial should be stopped.

The investigator also has the right to stop the trial. This could be because of the closure of the site. See 10.5 for details.

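### A patient who moves to surgery can supply a value to both samples of an independent-groups test, and the carried-forward control score can favour surgery

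*Protocol*

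**What the plan says.** Section 4.1 lets non-operated patients move to surgery at any time and sets no rule for the move. Sections 3.1 and 4.1 expect at most about one such patient in five years. Section 9.7 adds: "The number of patients is fixed at 30 in the operated group and at 10 in the non-operated group".

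The handling of a switcher is spread over several sections:

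- **7.1.1** moves the patient to the other arm and then rules: "Data collected up to this point will be used in the first treatment group and then data will be generated in the second treatment group". The same section lists the wish to change among the criteria for permanent discontinuation and then says that the patient can continue.
- **7.1.3** treats the move as the start of the trial for that patient. It does not say which score becomes the operated baseline.
- **9.2.2** names switching as an intercurrent event of the primary estimand and rules: "Data obtained until the event will be included in the analysis, last observation will be included in the evaluation".
- **9.3**, for the secondary objectives: "Patients changing to the operated group will be analyzed up to the date of change in the non-operated group".
- **9.2.1** has the change from baseline "compared by two-sided t-test for independent groups when data are normally distributed or with the Mann-Whitney-U-test", and closes: "There will be no adjustment made and no model fitting".
- **3.2** counts switching as an intercurrent event for progression to TKA. **3.3**, for the same outcome, lists only: "Intercurrent event: lost to follow-up, premature death".

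**The concern.** The t-test and the Mann-Whitney test both assume that the two samples come from different people. Under 7.1.1 a switcher can give one change score as a control and another as an operated patient, and nothing in the plan accounts for the pairing.

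Direction is the second issue. Section 2.2 says that non-operated patients risk losing knee function and can limit that risk by changing group. Section 4.1 mentions the change directly after describing progression of osteoarthritis. If a patient moves at a low point, 9.2.2 keeps that low score as the control result. The operated baseline is then taken at or near the same low point, so part of any ordinary recovery counts as improvement after surgery. Both effects would widen the difference in favour of surgery. With 10 controls, one patient is 10% of the group (12.5% of the 8 left after 20% loss).

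**Working it through.** **Group sizes and the plan's own figures.** Section 9.8 rests on 10 and 30 separate people. At effect size 2.0, an exact two-sided noncentral t calculation gives power 0.9935 for 10/30 at alpha 0.00655 (stated 0.993) and 0.9857 for 8/24 at alpha 0.014 (stated 0.985). Both are reproduced. Neither makes room for a person counted twice.

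**Spread.** The protocol states no SD, so a change SD of 10 to 20 points is an assumption. As a plausibility check, effect size 2.0 implies an SD of 20/2.0 = 10 for the 20-point target, (84 − 55)/2.0 = 14.5 for IKDC and (86 − 46)/2.0 = 20 for KOOS, if controls do not change.

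**Formula.** Suppose that the score at the switch lies d points below the patient's usual level, that the dip is temporary, that the same score is reused as operated baseline, and that the switcher is added to 30 operated patients.

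- Control mean too low by d/10.
- Operated mean change too high by d/31.
- Bias = d/10 + d/31, which is 1.3, 2.6 and 4.0 points for d = 10, 20 and 30.
- Share from the control side: (1/10)/(1/10 + 1/31) = 0.1/0.1323 = 76%.

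**Simulation.** No surgery effect, switch after the 12-month visit, change SD 10 to 20, between-patient SD 12, two-sided t-test at 0.05, 20,000 runs per setting. Ranges cover 10/30 and 8/24. The nominal false-positive rate in favour of surgery is 2.5%.

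| Who switches | Operated baseline | Bias towards surgery (points) | False positives for surgery |
|---|---|---|---|
| 1, worst change | reused | 1.0 to 2.3 | 4.1% to 4.5% |
| 1, worst change | newly taken | 0.8 to 1.8 | 3.6% to 3.8% |
| 2, worst change | reused | 1.7 to 3.8 | 5.9% to 6.3% |
| 3, worst change | reused | 2.1 to 4.5 | 7.7% to 8.1% |
| 3, worst change | newly taken | 1.6 to 3.4 | 5.7% to 6.2% |
| 1 to 3, unrelated to score | reused | about 0 | 2.5% to 3.1% |

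At 10/30 alone, one worst-case switcher with a reused baseline gives 1.0 to 2.0 points. The last row isolates the breach of independence: the switcher's two change scores correlate at about −0.5, and the cost in error rate is slight. With a newly taken baseline and unrelated switching, the correlation is about 0.

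**Milder selection.** In a separate run of 8,000, patient-level and visit-level SDs were 10/10, 14/14 and 12/8. When the worst-scoring control switches, the bias is 1.5, 2.1 and 0.9 points. When a random control from the worse half switches, it is 0.7, 0.9 and 0.4 points, with a two-sided error of 0.048 to 0.054.

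**What single entry removes.** In the same three settings, counting the switcher once but keeping the carried-forward control score leaves 1.1, 1.6 and 0.7 points. That is 73%, 76% and 78% of the bias, in line with the 76% above. If the switcher stays in the non-operated group with the observed 24-month score, the bias is −0.05 to +0.04 points and false positives for surgery are 2.3% to 2.6% (8,000 runs per setting, change SD 14, no surgery effect).

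**The case against.** The strongest reply is that much of the harm is inferred.

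- **Poor scores.** No section says that switchers score badly. Section 4.4 lets pregnant women join the non-operated group, a route to later surgery that need not depend on score. This stands as a limit: the link to deterioration in 2.2 and 4.1 makes selection plausible, not certain.
- **Reused baseline.** A reader might infer that the last control score becomes the operated baseline. The plan does not say so. Section 7.1.3 restarts the trial and 1.3 collects scores at screening, so a new baseline is at least as natural. The bias is then smaller but remains if badly-off patients switch.
- **31 versus 10.** A reader might infer these sizes. Section 9.7 fixes 30 and 10 without mentioning switchers, and a patient who moves during the two-year recruitment could fill one of the 30 places.
- **Always towards surgery.** Sections 1.2 and 12.1 describe slow progression, expected more often without surgery. If the decline is real, carrying the score forward stops the control's record before further loss, which can work against surgery. This stands, so the direction is likely but not fixed.
- **TKA.** A reader might infer that the plan assigns a TKA after a switch in conflicting ways. Sections 7.1.1 and 9.3 agree: non-operated up to the change. Section 3.3 only leaves switching off its list. If the 2.5% in 11.1 applied to one switcher, 0.025 events would be expected. What remains is a gap in wording.

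None of these replies touches the core. The same person's data go to both groups, and the named test does not allow for it.

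**Conclusion.** The point holds on the text. Sections 7.1.1, 9.2.2 and 9.2.1 together let one person supply a value to each sample of an independent-groups test, with the last pre-switch score standing as the control result. This can favour surgery if patients switch because they are doing badly.

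At the protocol's expectation of one switcher, the bias is about 1 to 2 points when the worst control switches (assumed change SD 10 to 20), less under milder selection and about 0 when switching is unrelated to score. Against a 20-point target this is small and would not by itself overturn a result of the expected size. It grows with each further switcher, and 4.1 sets no rule that would keep the number at one.

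The statement that the plan reuses a poor score as baseline and so always favours surgery goes beyond the documents. The correction is still worth making before data are seen, because the unblinded investigator is also sponsor and analyst.

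**What to change.** - **Sections 7.1.1, 9.2.2 and 9.3:** state that each patient enters every between-group comparison once, in the group chosen at enrolment. List a switcher's post-surgery efficacy data separately, with the baseline used, and keep them out of the operated-group mean. Put the safety data after surgery into the operated group's safety tables.
- **Beside the main result:** single entry leaves the carried-forward control score in place. Report an analysis in which the switcher stays in the non-operated group with the observed 2- and 5-year values, and note that this dilutes the difference if surgery works. Section 1.3 times visits from surgery and 7.1.3 restarts the trial, so say that scores at 2 and 5 years after enrolment are still collected.
- **Section 3.3:** add switching to the intercurrent events with the same rule as in 3.2, so that the TKA curves treat a switcher in one way.
- **Section 7.1.1:** reconcile the listing of switching under permanent discontinuation with the statement that the patient continues.

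The cost is a few sentences, one extra analysis and possibly one or two extra questionnaires for a switcher. About one late operated case is not pooled into the efficacy mean.

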7.1.2 Temporary Discontinuation or Interruption of Trial Intervention

This is an orthopedic trial. The surgery is the start point and after the surgery there are no treatments. There are only follow-up visits, which include an MRI and 3 questionnaires (IKDC, KOOS, CRF)

If the patient cannot attend a post-surgical visit at the time envisaged it is possible to do the visit later/earlier. For this there are time ranges given which is as follows:

- U1: at the end of hospital stay (only for operated patients)
- U2: 6 weeks after surgery (\pm 4 days, only for operated patients)
- U3: 6 months after surgery (\pm 1 months, for operated patients, for non-operated patients only PROMs)
- U4: 12 months after surgery (\pm 1 months, for operated patients, for non-operated patients only PROMs)
- U5: 24 months after surgery (\pm 1 months)
- U6: 5 years after surgery (\pm 3 months)

If for any reason this time slots cannot be used by the patient e.g. because of a pandemic or another major event, then the next time slot will be used.

Thus, a temporary discontinuation of the trial is not a problem, because no treatment occurs after surgery, but should be avoided.

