8.3. Safety Assessments and Procedures

This is a low intervention trial. This trial poses a minimal additional risk to subject safety compared to normal clinical practice (CTR, page 2 (11)).

As described under 8.2 there is a close-meshed follow-up schedule, for operated patients, which will also evaluate the patient's safety. The highest risk that safety issues occur is during surgery. But the surgery is an established method. All safety measures will be taken during surgery as for every surgery, not being a clinical trial. The first visit at the end of the hospital stay is one of the safety measures for the patient. Before the patient leaves the hospital, the patient will be checked, if there are no issues which may affect his/her safety. AE, SAE and SUSARs are recorded in the electronic patient chart and will be recorded in the CRF.

AE will only be recorded in the electronic patient chart and in the CRF. When AEs affecting the conduct of the trial and/or increasing the risk to the subject, the IRB/IEC should be promptly informed by a written

report.

SAE: because the investigator and sponsor is the same person in this trial, information to the sponsor is immediately. The SAE will be recorded in the electronic patient chart and in the CRF. Unless the protocol waives the notification, the investigator reports the SAE to the ethic committee and to the local authorities (Bundesoberbehörde) immediately but at least within 15 days, after becoming aware of it. If the investigator does not have all the information by then, the missing information must be submitted as soon as possible.

SUSARs: The investigator/sponsor shall inform the competent higher federal authority, the lead ethics committee, and the competent authorities of other Member States immediately, but at the latest within 15 days of becoming aware of a SUSAR. The deadline is reduced to 7 days if an unexpected serious adverse reaction is life-threatening or has led to death.

There are no laboratory investigations part of the trial.

There is no independent Data Monitoring Committee. Clinical monitoring will be performed from an independent clinical monitor for the safety of the patients. The extend and nature of the monitoring will be adapted due to Article 48 CTR.

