8.4.2 Time Period and Frequency for Collecting AE and SAE Information

At each follow-up (at the end of the hospital stay, after 6 weeks, after 6, 12 and 24 months and after 5 years, for the operated group and after 6, 12, 24 months and 5 years for the non-operated group) AE and SAE are collected regularly. Since the patient can inform the investigator about AE, or SAE at any time, collecting AE and SAE are performed as soon as known by the investigator. After finishing the trial, the investigator is still reachable for the patient to inform him about any AE or SAE.

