9.1 Analysis Sets

Full analysis set will be performed.

PROMs:

Change from baseline for the PROMs (IKDC, KOOS, VAS-pain score) for the operated/non-operated group after 6, 12 and 24 months and 5 years and between groups.

Complications, AE, SAE and SUSARs:

The number of complications, AE, SAE and SUSARs will be evaluated at each time point and compared between the groups with Fishers exact test.

MRI evaluation:

Change in MRI evaluated using the Outerbridge [1] graduation, the size of the meniscal defect and the meniscus itself, the MRI signal of the meniscus will be evaluated after a modified score after Genovese et al.[32] and the number of patients with an extrusion and the size of the extrusion.

Patient satisfaction:

Patient satisfaction will be categorized as: very pleased, pleased, not pleased, very unsatisfied and will be evaluated using the Chi-square test.

Progression of osteoarthritis up to TKA:

The number of patients with progression of osteoarthritis up to TKA for both groups will be compared with a Kaplan-Meier time to event curve.

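### Harms are to be tested between groups at every time point, but controls have no discharge or 6-week visit, and the protocol contradicts itself on whether their adverse events are collected at 6 and 12 months

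*Protocol*

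**What the plan says.** Safety is a secondary objective (Section 3.2). Section 9.1 states the analysis: "The number of complications, AE, SAE and SUSARs will be evaluated at each time point and compared between the groups with Fishers exact test". Section 9.5 repeats a group comparison by Fisher's test.

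Section 8.4.2 schedules AE and SAE collection "at the end of the hospital stay, after 6 weeks, after 6, 12 and 24 months and after 5 years, for the operated group". Controls are given four of these six occasions, the first of them at 6 months. Sections 6.1, 7.1.2 and 7.3 agree that controls have neither the discharge visit (U1) nor the 6-week visit (U2).

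For the 6- and 12-month visits (U3, U4), Section 7.1.2 adds "for operated patients, for non-operated patients only PROMs". Section 8.3.1 requires a physical examination at each visit, with no exception for controls.

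Section 7.1.1 places follow-up MRI "after 6 weeks, 6, 12, 24 months and 5 years in the operated group". Controls are scanned only at the 24-month and 5-year visits, and Section 9 agrees. Table 1 in Section 6.1 instead puts MRI at each follow-up visit, marked yes for both groups.

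**The concern.** A between-group test of harms means something only where both groups are observed in the same way. Here the test is promised at time points where one group is not scheduled to be seen. At two of the shared visits the protocol gives conflicting accounts of what is done for controls. If the site follows Section 7.1.2 literally, controls are not asked about adverse events until 24 months, although Section 8.4.2 says they are asked at 6 and 12 months. Any cumulative count would then mix a true difference in harm with a difference in how often patients were asked. A later analysis plan cannot recover events that nobody asked about, so the collection wording has to be settled in the protocol.

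**Working it through.** **Step 1. Count the scheduled AE contacts.**

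| Visit | Operated (8.4.2) | Controls (8.4.2) | Controls (7.1.2, literal) |
|---|---|---|---|
| Discharge (U1) | yes | no | no |
| 6 weeks (U2) | yes | no | no |
| 6 months (U3) | yes | yes | PROMs only |
| 12 months (U4) | yes | yes | PROMs only |
| 24 months (U5) | yes | yes | yes |
| 5 years (U6) | yes | yes | yes |
| Total | 6 | 4 | 2 |

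Two of the six time points (U1, U2) have no control data on any reading. Under Section 8.4.2 controls have 4/6 = 67% of the operated group's contacts; under the literal reading of Section 7.1.2 they have 2/6 = 33%. In the first six months under Section 8.4.2 the count is three against one. At the four shared visits taken one by one it is equal, provided Section 8.4.2 governs.

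**Step 2. Count the follow-up MRIs.** Under Sections 7.1.1 and 9, operated patients have five and controls two. Table 1 in Section 6.1 would give controls an MRI at all four of their visits. The schedule in Section 1.3 uses grey shading for operated-only items. That shading does not survive in the text available here, so it cannot settle what controls receive.

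**Step 3. Can the bias be sized?** Not from the protocol, which gives no AE rate. What follows is an illustration on stated assumptions.

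Inputs: 30 operated and 10 control patients (Section 9.7); two-sided Fisher's test at 0.05. Assumed: the same true risk r in both groups, all operated events recorded, and a share s of control events recorded. The values s = 67% and 33% take the share of contacts as the share of events found, which is itself an assumption; 50% lies between.

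False rejection = sum over i = 0..30 and j = 0..10 of Bin(i; 30, r) × Bin(j; 10, r·s), counting only tables with Fisher p < 0.05.

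Spurious risk difference = r(1 − s).

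Each cell gives false rejection, then the spurious risk difference in percentage points:

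| True risk r | s = 67% | s = 50% | s = 33% |
|---|---|---|---|
| 10% | 0.6%; 3.3 | 0.3%; 5.0 | 0.1%; 6.7 |
| 20% | 1.9%; 6.6 | 2.3%; 10.0 | 3.1%; 13.4 |
| 30% | 5.1%; 9.9 | 8.8%; 15.0 | 15.2%; 20.1 |
| 50% | 8.8%; 16.5 | 19.3%; 25.0 | 37.8%; 33.5 |

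With equal detection (s = 100%) the same enumeration gives 1.7% to 2.8% across the four risks. Inflation beyond 5% therefore needs common events, at about 30% risk or more. At 10% to 20% risk, ten controls are too few for the test to reject often. The estimated risk difference is biased in every cell.

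**The case against.** The strongest reply is that the phrase in Section 7.1.2 means no MRI for controls at 6 and 12 months. That section is a list of visit windows, its surrounding text describes visits as an MRI plus questionnaires, and the reading fits the MRI schedule in Sections 7.1.1 and 9. Section 8.4.2, the safety section, schedules AE collection from controls at those visits, and Section 8.3.1 requires an examination. This is probably the intended meaning, and it makes the 33% column the less likely case. It does not remove the contradiction, because the protocol nowhere says so, and it leaves the two empty comparisons as they are.

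Three further points stand in part. Reports are accepted from any patient at any time (Section 8.4.2), and a 6-month visit can ask about the whole preceding interval, so a missed contact is not a missed event. Serious events such as hospitalisation or death depend little on visit count. And the protocol itself says "The highest risk that safety issues occur is during surgery"; its listed trial-related events (Section 12.1) include redness, haematoma and swelling, so part of any early excess is true surgical harm. All this softens the bias without removing it.

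A reader might also infer that MRI finds complications in operated patients that cannot be found in controls. The documents do not support that as a bias in the AE comparison. MRI findings are a separate secondary endpoint, nothing in the protocol makes an MRI finding an adverse event, and the MRI schedule is itself contradictory.

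**Conclusion.** The point holds as a defect of wording and analysis with a cheap remedy. Two parts rest on the text alone: two of the six promised comparisons have no control data, and Section 7.1.2 conflicts with Sections 8.3.1 and 8.4.2 on the 6- and 12-month control visits. The six-to-four imbalance in cumulative contacts follows by counting.

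The size of the bias is unknown. Depending on assumed event risk and detection, false rejection runs from 0.1% to 37.8%, so quoting the upper end alone would mislead.

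Three stronger readings are not supported. That controls go unassessed for adverse events until 24 months rests on the less likely reading of Section 7.1.2. That an early table such as 15/30 against 0/10 would give a spurious significant result (p = 0.006) counts unobserved controls as event-free and ignores real surgical harm; without control visits no such table can be formed. That no safety result could be interpreted goes too far, because under Section 8.4.2 the four shared visits have equal scheduled contacts.

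**What to change.** 1. Reconcile Section 7.1.2 with Sections 8.3.1 and 8.4.2, so that controls at 6 and 12 months get the same AE and complication questions and the same examination as operated patients. If the phrase means that there is no MRI, say so, and bring Table 1 in Section 6.1 into line with Sections 7.1.1 and 9.
2. In Section 9.1, report discharge and 6-week events for the operated group alone, with exact confidence intervals.
3. Restrict the between-group Fisher comparison to patients with at least one event recorded at the shared visits (6, 12 and 24 months, 5 years). State which period the 6-month question covers, the same in both groups.
4. State beside the results that operated patients had extra early contacts and MRIs.

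Cost: protocol wording and a few minutes at control visits that Sections 6.1 and 7.3 already schedule. There is no p-value at the two early time points. Because the shared-visit comparison can leave out perioperative events, it must be read together with the operated-only table and not as the full account of surgical harm.
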